7.1.3. Additional Safety Assessments

Additional safety measures will be summarized for the Safety analysis set. Only data in the study eye will be presented in tabulations. Data may be tabulated by visit and/or for the overall study period (i.e. subjects with at least one finding during the study period) as indicated. Summaries for the overall study period will include data from unscheduled visits.

The change in safety data may be summarized by study period as indicated. In general, only the CFB will be presented for visits belonging to the initial study period and both the CFB and the CFPE will be presented for visits belonging to the PE study period.

The criteria for clinical significance varies by measure. Unless otherwise specified,

- [REDACTED]
- [REDACTED]

7.1.3.1. Visual Acuity

Best spectacle corrected visual acuity (BSCVA) is measured at Screening using the Early Treatment Diabetic Retinopathy Study (ETDRS) letter chart. Corrected VA (ETDRS) is collected at Week 4, Month 6, Month 12, Month 18, Pre-Exchange, and Week 4 PE unless a decrease of 2 or more lines (≥ 10 letters) from Screening occurs, at which time BSCVA is also measured. Pinhole VA (Snellen) is collected at the Day 1, Day 10, Day 1 PE and Day 10 PE visits.

Corrected VA and BSCVA will be presented in tabulations. If both corrected VA and BSCVA are collected, only BSCVA will be presented in the tabulations.

The worst change in VA will be summarized [REDACTED] for the total, initial, and PE study periods. The worst change in VA is defined as the largest decrease, or smallest increase if there is no decrease, in number of letters read correctly across all

postoperative visits (scheduled or unscheduled) in the study period. For the initial and total study periods, only the worst CFB will be presented. For the PE study period, the worst CFPE will also be presented. The number and percentage of subjects with a worst decrease of greater than or equal to 15 letter (3 lines) will also be summarized for each study period.

The actual and CFB in number of letters read correctly will be summarized by visit [REDACTED]. The number and percentage of subjects with a decrease of greater than or equal to 15 letters (3 lines) will also be summarized by visit [REDACTED]. For visits belonging to the PE study period, the CFPE will also be summarized both continuously and categorically as outlined.

A visual acuity subject listing will be provided for all visual acuity data including pinhole VA.

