6.3.3 PREOPERATIVE PROCEDURES

6.3.3.1 Visit 1 (Screening)

- 1) Written informed consent.
- 2) Assign subject number.
- 3) Demographics, medical and surgical history, current ocular and systemic conditions, prescription medications, and medications known or suspected to lower IOP.
- 4) A pregnancy test (if applicable) may be administered at any time during this visit.

CLINICAL PROTOCOL

Date:
September 18, 2019

Protocol No.:
IDOS-402-IVIV

- 5) Measure best spectacle corrected visual acuity through manifest refraction (ETDRS) in each eye.
- 6) Perform slit-lamp biomicroscopy (including crystalline lens).
- 7) Measure IOP (can be measured at any time) and record the time.
- 8) Pachymetry.
- 9) Perform a gonioscopic examination.
- 10) Perform a dilated ophthalmoscopy/fundus examination.
- 11) Assess optic nerve abnormality (ophthalmoscopy).
- 12) Assess vertical C/D ratio.
- 13) Review screening inclusion and exclusion criteria. Do not continue screening any subject who does not meet the screening eligibility requirements.

If the subject is qualified:

- 1) Schedule the subject for Visit 2 (First Operative Day 0).
- 2) [REDACTED]
- 3) Advise the subject to discontinue taking their topical hypotensive medication beginning the morning of visit 2 (First Operative Day)
[REDACTED]

If the subject is ineligible for the study, complete the appropriate CRF.

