6.3.4.10 Visit 10 (Week 4 Post-Exchange Exam, 28 days ± 3)

- 1) Update subject's medical status and concomitant medications.
- 2) Assess study eye adverse events.
- 3) Measure corrected visual acuity (ETDRS). A manifest refraction and best spectacle corrected visual acuity (ETDRS) should be performed if corrected VA (ETDRS) has decreased by 2 or more lines (≥ 10 letters) from Visit 1 (Screening).
- 4) Perform slit-lamp biomicroscopy
- 5) Measure IOP (can be measured at any time) and record the time (observer).
- 6) Perform a gonioscopic examination.

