2.4. Sample Size Determination

The sample size of 210 subjects who undergo implantation and exchange of a Travoprost Intraocular Implant was determined to support the study objectives and is not based on statistical power calculations. [REDACTED]

[REDACTED]

3. Analysis Sets

For the purposes of analysis, the following analysis set is defined:

Subject Analysis Set	Description
Safety analysis set	
• All subjects who receive an implant.

The safety analysis set will be used for all data tabulations and listings.

4. General Statistical Considerations

Demographic and safety data collected on the case report forms (CRFs) will be displayed in tabulations and data listings. Only data from scheduled visits will be used in tabulations unless otherwise specified. In general, summary tables will be presented [REDACTED] [REDACTED]. Data may also be summarized by study period if indicated. Data listings will present data either recorded on or derived using the CRF. [REDACTED] [REDACTED]

No formal statistical testing will be performed. All data summaries [REDACTED] will be performed using SAS® software, Version 9.4 or higher.

Continuous data will be summarized using the number of observations, mean, standard deviation, median, minimum, and maximum. Continuous data may also be dichotomized, or otherwise split, into clinically meaningful categories and may be further analyzed as categorical data as specified in the individual endpoints.

Categorical data will be summarized using frequency counts and percentages. Unless otherwise stated, subjects with missing visit data will be omitted from both the numerator and denominator of such calculations.

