4.1.3. Change from Baseline/Pre-Exchange

The change from baseline (CFB) and the change from pre-exchange (CFPE) values are calculated as

- CFB value = follow-up visit value – baseline value.
- CFPE value = follow-up visit value – pre-exchange value.

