2.3. Study Design

This is a prospective, non-randomized, open-label, single center trial evaluating [REDACTED] [REDACTED] the performance of the Travoprost Intraocular Implant in subjects with open-angle glaucoma (OAG) or ocular hypertension (OHT). Approximately 210 total subjects (14 cohorts of 15 subjects) will be enrolled into the study. Subjects will be screened for qualification as per the inclusion/exclusion criteria (refer to Sections 6.2.1 and 6.2.2 of study protocol). Qualified subjects will be assigned to a cohort and will be implanted with the Travoprost Intraocular Implant (G2-TR-125 Implant) in one eye. Each cohort will consist of a specified duration [REDACTED]

[figure not shown]
[REDACTED] All enrolled subjects will undergo a second operative visit, the exchange of the Travoprost Intraocular Implant, at Visit 7. The duration of time for each cohort is the time between the implantation of the 1st implant at Visit 2 (Day 0) and the implantation of the 2nd implant at Visit 7 (Exchange procedure and collection of the aqueous humor and explant).

Depending on the cohort assignment, subjects will be followed for 4 – 25 months postoperatively (3 – 24 months after 1st implantation and 4 weeks after the 2nd implantation). Study follow-up will continue until the Week 4 post-exchange (PE) visit.

Depending on the cohort assignment, the study consists of 10 to 13 visits: Visit 1 (Screening), Visit 2 (First Operative Day 0), Visit 3 (Day 1), Visit 4 (Day 10), Visit 5 (Week 4), Visit 5.1 (Month 6), Visit 5.2 (Month 12), Visit 5.3 (Month 18), Visit 6 (Pre-Exchange Exam, within 10 days prior to Visit 7), Visit 7 (Second Operative/ Exchange), Visit 8 (Day 1 post-exchange [PE]), Visit 9 (Day 10 PE), and Visit 10 (Week 4 PE). Subjects will exit the study at the conclusion of the Week 4 PE visit.

All subjects will have visits at post-operative Day 1, Day 10, Week 4, pre-exchange, and post-exchange Day 1, Day 10, and Week 4. Table 1 summarizes the remaining visits for each cohort along with other cohort information. Appendices A-G show the schedule of visits and measurements for each cohort.

Subjects will be assigned to their cohort sequentially as defined by the cohort order as they receive surgery. Each cohort must be filled prior to starting the next cohort.

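### Visual acuity change from pre-exchange can subtract corrected VA from BSCVA, because the tabulated method depends on the reading and no same-method rule is set

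*SAP*

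**What the plan says.** **Baseline.** Protocol 6.3.3.1 (Screening): "Measure best spectacle corrected visual acuity through manifest refraction (ETDRS) in each eye". The baseline value is therefore a refracted BSCVA.

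**Follow-up.** Corrected VA is measured at Week 4, Months 6, 12 and 18 where scheduled, Pre-Exchange (Visit 6) and Week 4 post-exchange (Visit 10). Under Protocol 6.3.4.10, a manifest refraction and BSCVA "should be performed if corrected VA (ETDRS) has decreased by 2 or more lines" (10 letters or more) from Screening. The same trigger applies at the other corrected-VA visits. It stays tied to Screening after the exchange.

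**What is tabulated.** SAP 7.1.3.1: "If both corrected VA and BSCVA are collected, only BSCVA will be presented in the tabulations".

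**How change is formed.** SAP 4.1.3: "CFPE value = follow-up visit value – pre-exchange value". Neither that section nor the baseline and pre-exchange definitions (SAP 4.1.1 and 4.1.2) names a VA method.

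**What is reported after exchange.** Change from baseline (CFB) and CFPE are both summarised, as means and as losses of 15 letters or more. On worst change, SAP 7.1.3.1 adds: "For the PE study period, the worst CFPE will also be presented". All VA values are also listed.

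**The concern.** Which measurement enters the table depends on how poor the reading was. The trigger looks back to Screening, while CFPE looks back to Visit 6. An eye just above the trigger at Visit 6 and below it at Visit 10 has its post-exchange value replaced by BSCVA, while its pre-exchange value stays as corrected VA. If BSCVA is the better of the two, part of the loss across the exchange disappears from the CFPE table.

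Protocol 8.1 justifies the 210 subjects as adequate to inform on the safety of the exchange procedure. CFPE is the VA summary that isolates that procedure. CFB at the same visits also carries any change over the preceding 3 to 24 months.

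**Working it through.** The plan states no VA figure to reproduce. I coded the rule, worked single eyes by hand, and then simulated it.

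**Rule.** Let S be BSCVA at Screening, and C and B be corrected VA and BSCVA at a visit, all in letters. The tabulated value is R = C if S − C < 10, otherwise R = B. Then CFPE = R(Visit 10) − R(Visit 6), and CFB = R − S.

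**Error against corrected VA at both visits.** Reported CFPE minus corrected-VA CFPE equals (B − C at Visit 10, if triggered there) minus (B − C at Visit 6, if triggered there).
- Neither visit triggers: error 0.
- Both trigger: CFPE is BSCVA to BSCVA, which is like for like.
- One triggers: the gap at that visit enters in full.

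**Switch at Visit 10 only.** S = 80. At Visit 6, C = 71 (9 below, no refraction). At Visit 10, C = 56 and B = 64.
- Reported CFPE: 64 − 71 = −7.
- Corrected VA at both visits: 56 − 71 = −15.
- The 15-letter CFPE loss is missed. CFB = 64 − 80 = −16 is flagged.

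**Switch at Visit 6 only.** S = 80. At Visit 6, C = 69 (11 below) and B = 80. At Visit 10, C = 72 (8 below).
- Reported CFPE: 72 − 80 = −8.
- Corrected VA at both visits: 72 − 69 = +3. Loss is overstated.

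**15-letter category from baseline.** If B is at least 15 below S and C is no better than B, the trigger has fired and B is tabulated. If the trigger has not fired, the tabulated loss is under 10. An integer grid (S = 80, gaps 0 to 20) gave no misclassification.

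**Simulation inputs (assumptions, not in the documents).**
- The gap B − C is the same before and after exchange. It is 0, exponential with mean 2 or 4, or max(N(2,3),0) or max(N(4,4),0), whose means are about 2.5 and 4.3.
- Every reading has independent normal error, SD 3 or 4 letters.
- There is no true change from Screening to Visit 6.
- One million eyes per setting.

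**Share of eyes with a true 15-letter loss that CFPE flags as 15 letters or more**

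| Gap | SD 3 | SD 4 |
|---|---|---|
| 0 | 46.5% | 46.2% |
| exponential, mean 2 | 34.5% | 38.5% |
| max(N(2,3),0) | 32.6% | 37.0% |
| exponential, mean 4 | 30.6% | 35.3% |
| max(N(4,4),0) | 28.4% | 33.5% |
| one method at both visits | 50% | 50% |

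The 50% is exact: one-method CFPE is symmetric about −15. A true 15-letter loss is the relevant scenario. With a smaller true loss, every 15-letter flag is measurement noise.

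**Other results from the same runs**
- No true loss: mean CFPE is 0.0, as it must be because the two visits are then exchangeable. Between 2% and 18% of eyes still change method between visits.
- Mean CFB at Visit 6 with no true change: −1.2 to −2.7 letters with a gap, and +0.1 to +0.2 with none.
- CFB loss of 15 letters or more, true loss 15: flagged in 46% to 49.5%, against 50% for BSCVA at both visits.

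**The case against.** **Confirming a loss by refraction is sensible, and Protocol 4.2 names BSCVA as the safety variable.** This stands as a reason to keep the BSCVA-based table. It does not justify subtracting one measure from the other. The protocol synopsis and SAP 2.2 list corrected visual acuity instead, so the documents name both.

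**A reader might infer that loss after exchange is always understated.** The documents do not support that. CFPE is like for like when neither or both visits trigger, the error reverses when only Visit 6 does, and mean CFPE has no bias without true loss. Eyes already well below Screening before the exchange will usually trigger at both visits.

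**A reader might infer that follow-up VA is measured in old glasses or without refraction.** Corrected VA is never defined. It could use the Screening refraction, so the gap might be near zero. Even then some shortfall remains (about 46% against 50%), because only low readings are replaced by a second reading. That part is selection on a noisy trigger, not a difference between methods.

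**Other tables limit the harm.** CFB is reported at post-exchange visits, its 15-letter category holds up, and all VA values are listed. In the first worked eye CFB catches the loss. This lowers the stakes but does not correct the CFPE table.

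**The study is descriptive.** The SAP says "No formal statistical testing will be performed", and the sample size "was determined to support the study objectives and is not based on statistical power calculations". So no test or power statement is affected.

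**Conclusion.** The point holds in limited form. As written, the SAP can produce mixed-method CFPE values in either direction. For a true large loss at the exchange, in an eye previously near its Screening acuity, the net effect is to understate it: about 28% to 47% of true 15-letter losses are flagged, against 50%. That range rests on assumed mean gaps of about 0 to 4 letters, a per-reading SD of 3 to 4, and a gap that does not change at exchange. The documents supply none of these and no expected rate of such losses, so the number of subjects affected cannot be given.

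Mean CFB compares corrected VA, without a new manifest refraction, with a refracted baseline in every eye that does not trigger. If a gap exists it overstates loss, which is the cautious direction for safety. A broader claim that change from baseline is unreliable would go too far, since its 15-letter category is nearly unaffected.

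**What to change.** Amend SAP 7.1.3.1 before database lock, which the SAP introduction allows:

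1. Add CFPE (mean, worst and loss of 15 letters or more) computed on corrected VA at both visits. Corrected VA is scheduled at Visits 6 and 10 in every cohort and is still recorded when BSCVA is added.
2. Keep the planned BSCVA-based tabulation beside it.
3. Report the number of subjects whose tabulated method differs between the two visits, split by which visit used BSCVA.
4. Label mean CFB as mixed-method. Corrected VA is not scheduled at Screening, so a like-for-like mean cannot be recovered for eyes that never trigger.

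The cost is a few table rows from data already planned. The protocol's refraction rule stays as it is. The corrected-VA rows may count purely refractive change as loss. The BSCVA rows beside them will help to show where that has happened.

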7.1.3.2. Slit Lamp Examinations

Slit lamp measures collected on the CRF include corneal edema, corneal opacity, epithelium, endothelium, guttata, anterior chamber depth, anterior chamber cells, anterior chamber flare, and pupil. All slit lamp measures are collected at Screening and each postoperative visit within both study periods (Day 1, Day 10, Week 4, Month 6, Month 12, Month 18, Pre-Exchange, Day 1 PE, Day 10 PE, and Week 4 PE).

For each measure, the number and percentage of subjects in each severity grade/category will be summarized by visit [REDACTED].

Slit lamp findings will also be summarized by time interval within each study period. For the initial study period, the time intervals will consist of after Baseline through Week 4, after Week 4 to Month 12, and after Month 12 to Month 24. For the PE study period, only the time interval of after pre-exchange to Week 4 PE will be summarized. The summaries will include the number and percentage of subjects with at least one clinically significant worsening during the specified time interval (including data from unscheduled visits) [REDACTED]. For the initial study period, only a clinically significant worsening from baseline will be presented. For the PE study period, both a clinically significant worsening from baseline and a clinically significant worsening from pre-exchange will be presented. [REDACTED]

[REDACTED] For findings not associated with a severity grade, a status change from normal/absent to abnormal/present at any postoperative visit during the time interval will be summarized.

All slit lamp data will be listed. Two additional slit lamp listings will be provided – one for subjects with a worsening from baseline and one for subjects with a worsening from pre-exchange. For each subject, the listings will present findings at each visit only for measures with either

- (1) at least one clinically significant worsening at any follow-up visit during the study for findings associated with severity grade or
- (2) a status change (i.e., a change from normal/absent to abnormal/present at a follow up visit) at any follow-up visit during the study for findings not associated with severity grade.

Other slit lamp findings will also be listed.

7.1.3.3. Lens Findings

Lens measures are collected at Screening and each postoperative visit within both study periods (Day 1, Day 10, Week 4, Month 6, Month 12, Month 18, Pre-Exchange, Day 1 PE, Day 10 PE, and Week 4 PE). Lens measures include lens status, posterior capsule opacification, nuclear lens opacity, cortical lens opacity, and posterior subcapsular lens opacity.

For each measure, the number and percentage of subjects in each severity grade/category will be summarized by visit [REDACTED]

Lens findings will also be summarized by time interval within each study period. For the initial study period, the time intervals will consist of after Baseline to Week 4, after Week 4 to Month 12, and after Month 12 to Month 24. For the PE study period, only the time interval of after pre-exchange to Week 4 PE will be summarized. The summaries will include the number and percentage of subjects with at least one clinically significant worsening for the specified time interval (including data from unscheduled visits) [REDACTED]. For the initial study period, only a clinically significant worsening from baseline will be presented. For the PE study period, both a clinically significant worsening from baseline and a clinically significant worsening from pre-exchange will be presented.

All lens data will be listed. Two additional listings of lens findings will be provided – one for subjects with a worsening from baseline and one for subjects with a worsening from pre-exchange. For each subject, the listings will present findings at each visit only for measures with at least one clinically significant worsening at any follow-up visit during the study. Other lens findings will also be listed. Lens status (phakic or pseudophakic) will be listed and not tabulated.

7.1.3.4. Ophthalmoscopy Examinations

Dilated fundus, nerve abnormality, and vertical cup-to-disc ratio assessments are evaluated at Screening. All ophthalmoscopy data will be presented in a listing.

7.1.3.5. Gonioscopy

Gonioscopy assessments are performed at Screening, Week 4, Month 6, Month 12, Month 18, Pre-Exchange, and Week 4 PE. Gonioscopy findings include goniosynechiae, angle rubeosis, and other angle abnormalities.

The number and percentage of subjects with gonioscopy findings will be provided by visit [REDACTED].

A summary of status change findings will be provided [REDACTED] for each study period. For the initial and total study periods, only the number and percentage of subjects with a status change from baseline will be provided by visit and for the overall study period. For the PE study period, the number and percentage of subjects with a status change from pre-exchange will also be provided by visit and for the overall study period.

All gonioscopy data will be listed by subject. Two additional listings will be provided – one for subjects with status change findings from baseline and one for subjects with status change findings from pre-exchange. For each subject, the listings will present findings at each visit only for measures with at least one status change at any follow-up visit during the study.

7.1.3.6. Implant Visibility

Implant visibility is collected at Week 4, Month 6, Month 12, Month 18, Pre-Exchange, and Week 4 PE. [REDACTED] implant visibility will be summarized discretely by visit for the following implant visibility categories:

- Original Target Position
- Anchored but Migrated
- Not Anchored (if implant visibility in original target position is reported as “No” and the implant is not “anchored but migrated”)

A data listing will be provided for all implant visibility data.

7.1.3.7. Corneal Pachymetry

Corneal pachymetry assessments are performed at Screening. All pachymetry data, including central corneal thickness (μm), will be presented in a listing.

7.1.3.8. Intraocular Pressure

IOP is assessed for safety and is measured at Screening and all postoperative visits within each study period (Day 1, Day 10, Week 4, Month 6, Month 12, Month 18, Pre-Exchange, Day 1 PE, Day 10 PE, and Week 4 PE). IOP measurements will be taken once daily, unless surgery is performed. At each visit, IOP may be collected at any time of the day.

The actual and CFB in IOP (mmHg) will be summarized by visit [REDACTED]. The number and percentage of subjects will also be tabulated by visit [REDACTED] for the following categories:

- IOP ≥ 30 mmHg
- IOP Increase ≥ 10 mmHg

For visits belonging to the PE study period, the CFPE will also be summarized both continuously and categorically as outlined.

A subject listing presenting all IOP data will be provided.

8. Other Analyses

Other analyses will be summarized as outlined in the subsequent sections.

8.1.1. Operative and Surgical Analyses

[REDACTED]

